Treatment (Weeks 3-4): Participants randomized to the TAU group will continue to receive outpatient medical treatment of encopresis according to best practice guidelines by the pediatric gastroenterologist. In addition, participants in the TAU group will receive an individual appointment lasting up to 2-hours in clinic or via telehealth with a doctoral level clinician with extensive experience in behavioral treatments for encopresis. This outpatient appointment will include didactic presentation of a PowerPoint presentation and consultation regarding treatment of encopresis. During the appointment, the clinician will review strategies to increase continence. Specifically, the clinician will provide parent education on the following topics: how to collect and evaluate data on their child's bowel movements, how to establish and use a sit schedule, identifying behaviors that are precursors to bowel movements and how to use them to increase the probability of a bowel movement being continent, consequences for incontinence, and reinforcement for continence. These recommendations will be individualized based upon data collected during baseline. In addition, participants in the TAU group will continue to implement any medical treatment for constipation as prescribed.

Following the baseline phase, participants randomly assigned to the MIE group (i.e. 2 weeks) will begin treatment in the form of daily clinic visits or via telehealth (≤ 3 hrs./appointment) for 2 weeks (5 days/week). In addition, these participants will discontinue the use of medication prescribed for the treatment of constipation, other than the suppositories used in the MIE treatment. [RATIONALE: it is expected that participants will have daily bowel movements during the 2 weeks of MIE, and laxatives or other medicines may interfere with participants' ability to recognize and act upon the need to have a bowel movement (i.e., "pushing")]. During treatment all participants receiving MIE will be monitored for constipation and the pediatric gastroenterologist will be contacted to determine if additional medications are needed if more than three days pass without a bowel movement. At the conclusion of the clinic-based phase of treatment caregivers will be trained to implement MIE with $\geq 90\%$ fidelity to the protocol, and told to continue to use the procedures upon discharge.

Assessments during the randomized trial Assessment of therapeutic response and

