Home Implementation - After the MIE treatment phase, subjects will be given suppositories to utilize at home and a handout that addresses frequently asked questions about the use of suppositories. MIE treatment group subjects will leave with one of three planned regimens: one Glycerin suppository a day, two Glycerin suppositories a day or one Bisacodyl suppository a day. The determination of which group subjects are in will be made by the study team based on subject's response during MIE treatment. It is anticipated that most subjects will leave with the plan of one Glycerin suppository a day. Subjects in both the one Glycerin or one Biscaodyl suppository a day will be given a 30-day supply of study medication upon completing the MIE treatment phase (e.g. 30 suppositories). Subjects receiving two Glycerin suppositories a day will leave with enough medication to also last 30-days while taking two Glycerin suppositories (e.g. 60 suppositories). Note that subjects in the two Glycerin suppository group may only need to receive a single suppository if the child begins to have bowel movements after administration of one suppository.

Intervention Content

MIE consists of daily clinic appointments, each of which lasts until a bowel movement occurs or 3 hours elapse. Each appointment consists of a series of scheduled sitting routines (i.e., "sits") that last up to 32 min. Each sit consists of 10 min on the toilet, followed by 1 min of standing, then repeating the 10 min on the toilet 1 min off, for 30 cumulative minutes of sitting. The first sit is conducted prior to the administration of any medication to provide an opportunity for an independent continent bowel movement. If no continent bowel movement occurs, trained staff administer a dose of

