a liquid glycerin suppository to elicit a bowel movement, immediately followed by another sit to ensure any resulting bowel movement is continent. Any continent bowel movements result in immediate delivery of a potent positive reinforcer, identified previously via systematic preference assessments (Deleon et al., 1996). The appointment ends following a continent bowel movement. If a bowel movement is not observed the participant receives a 30 min break, followed by a second dose of the glycerin suppository. The participant is once again guided to complete the sitting routine following the second administration, with the same consequences for continence. After the third sit the appointment ends even if a continent bowel movement did not occur. Glycerin suppositories are replaced by bisacodyl if 2 or more days pass without a continent bowel movement using the liquid glycerin suppository. If bisacodyl is required it is administered prior to the second sit (i.e., after no bowel movement occurs on the opportunity for independent continence) to ensure that the medication has sufficient time to work prior to the end of the appointment. Medication fading occurs each time there are two consecutive days with continence by replacing bisacodyl with a glycerin suppository (if bisacodyl was necessary), and/or reducing the dose of the glycerin suppository by 50% until continent bowel movements occur independently during the first sit (i.e., without medication). Caregivers are trained to implement the toileting routine during the final two days of MIE until they demonstrate 90% fidelity with the protocol. Upon completion of MIE they are instructed to continue to implement the intervention until independent continence is achieved.

Subjects receiving MIE will be expected to receive a minimum number of treatment appointments prior to ending the MIE treatment phase. Subjects in the 2-week MIE treatment group will be expected to complete 10 MIE appointments within 17 days. This will ensure all subjects received an adequate level of treatment intervention prior to receiving parental intervention exclusively at home. Subjects who do not meet the minimum number of appointments within the time frame will be documented as protocol deviations.

Inclusion & Exclusion Criteria

Inclusion Criteria

1. Males and females \geq 5 years of age and \leq 12 years 11 months of age.

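### MIE children stop their prescribed constipation medicines, but the three-day trigger for gastroenterologist review is not carried through the home phase to Week 28

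*Combined protocol and SAP*

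**What the plan says.** All references are to the combined protocol and SAP.

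- **The stop.** Under Treatment (Weeks 3-4), MIE children begin daily clinic visits and "these participants will discontinue the use of medication prescribed for the treatment of constipation, other than the suppositories used in the MIE treatment". The bracketed rationale is that "it is expected that participants will have daily bowel movements during the 2 weeks of MIE", and that laxatives may get in the way of learning to push.
- **The safeguard.** The same paragraph continues: "During treatment all participants receiving MIE will be monitored for constipation and the pediatric gastroenterologist will be contacted" to decide on additional medicines if the child goes more than three days without a movement.
- **Discharge.** The next sentence reads "At the conclusion of the clinic-based phase of treatment caregivers will be trained to implement MIE", and caregivers are told to carry on with the procedures. Intervention Content adds that "they are instructed to continue to implement the intervention until independent continence is achieved".
- **Steps available at home.** Under Home Implementation, "MIE treatment group subjects will leave with one of three planned regimens": one glycerin, two glycerin or one bisacodyl suppository a day. Intervention Content has an escalation rule: "Glycerin suppositories are replaced by bisacodyl if 2 or more days pass without a continent bowel movement using the liquid glycerin suppository".
- **The comparator.** Treatment-as-usual (TAU) children "will continue to receive outpatient medical treatment of encopresis according to best practice guidelines by the pediatric gastroenterologist". Medical Assessment says that those who are constipated stay on constipation treatment through follow-up. For MIE it mentions medical treatment only in the baseline period.
- **The home phase.** Reminder Calls describes monthly scripted calls that check supply and offer no clinical guidance. Clinical intervention is named there only for an emergency. Table 2.0 schedules daily caregiver records in the Treatment phase, none in the 18-week No Contact phase, and daily records again in the two-week Follow Up.

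**The concern.** A rule that withdraws a medicine and the rule that rescues a child who needs it back should last equally long. Here the stop has no stated end, while the rescue rule is written for a limited period.

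The Background names long-standing constipation as the cause of encopresis in most affected children, and says it tends to return when toileting skills are not learned. The exposed child is therefore the MIE non-responder: off the earlier medicine, at home, with a suppository regimen that is not producing movements. In clinic, the gastroenterologist trigger sat on top of the suppository steps. At home the suppository steps continue, but the trigger is not restated. The caregiver on a glycerin regimen is not clearly given bisacodyl to step up to. The Consenting section also asks families to leave other medicines unchanged and report any change, which may discourage a family from restarting a laxative on its own.

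What is at stake is the safety of individual children and a clear instruction to staff and families.

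**Working it through.** The plan gives no figure for this point, so there is none to reproduce. The check is a reading of the text followed by date arithmetic.

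**Step 1: how long does the trigger run?**

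- *Narrow reading.* The sentence stands under a heading limited to Weeks 3-4, and the rationale for the stop covers only the two weeks of MIE. The trigger ends at clinic discharge.
- *Wide reading.* The following sentence speaks of a clinic-based phase of treatment, which implies that treatment also has a home part, and Table 2.0 has a Treatment phase of 8 weeks. Ending that phase at Week 8 fits the 28-week trial: 2 + 6 + 18 + 2 = 28 weeks.

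No section on home implementation, reminder calls or safety repeats the trigger, so on neither reading does it reach Week 28.

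**Step 2: inputs, in days from the Baseline Visit (day 0, the first MIE day).**

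- Week 8 visit: day 35 to 49, nominal 42 (Visit Windows).
- Week 28 visit: day 175 to 189, nominal 182 (Visit Windows).
- Clinic end, latest: day 17 (Intervention Content: 10 appointments within 17 days).
- Clinic end, earliest: day 11 (10 weekday visits with a Monday start). Any other weekday start ends on day 13.
- Clinic end, nominal: day 14 if two full weeks are counted, day 11 if the Monday start is taken as typical. Both are shown.

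**Step 3: days without the trigger after Week 8 (both readings).**

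- Nominal: 182 − 42 = 140
- Shortest: 175 − 49 = 126
- Longest: 189 − 35 = 154
- Of the nominal 140, 18 × 7 = 126 have no diary and 2 × 7 = 14 have one.

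**Step 4: further days before Week 8 (narrow reading only).**

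- Nominal: 42 − 14 = 28, or 42 − 11 = 31
- Shortest: 35 − 17 = 18
- Longest: 49 − 11 = 38

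The extremes of Steps 3 and 4 should not be added, because the Week 8 date enters both with opposite sign. From discharge to Week 28 the narrow-reading total is 175 − 17 = 158 to 189 − 11 = 178, nominal 182 − 14 = 168 or 182 − 11 = 171.

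**Step 5: sensitivity to Table 2.0.** If its 8 weeks ran in full from the Baseline Visit, Treatment would end on day 56. The uncovered stretch would be 175 − 56 = 119 to 189 − 56 = 133 days, nominal 182 − 56 = 126. The phases would then sum to 2 + 8 + 18 + 2 = 30 weeks (31 with a three-week baseline), which does not fit a 28-week trial. Even so, at least 119 days have no trigger.

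**The case against.** The strongest reply is that the child is not left without care, and that stands. MIE children go home on a suppository regimen, both products are sold over the counter, and the monthly calls confirm supply. The Safety Review asks about bowel function at each assessment visit. The Informed Consent section gives caregivers contact information for the principal investigator and the coordinator. The Adverse Event section provides for weekly-meeting discussion of possible deterioration, a clinical conference with the caregiver, and care decisions with the primary care provider. The limits on the scripted calls do not stop a family from telephoning. The suppository handout and the consent pages are not shown and may say when to call. A reader might infer that there is no safety oversight after discharge; the documents do not support that.

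Four other inferences also go too far:

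- *That the stop is permanent.* Its rationale is confined to two weeks and nothing forbids resumption. The text is silent, which is different.
- *That TAU has a trigger and MIE does not.* No days-without-movement rule is stated for TAU at any time. The contrast is that constipated TAU children keep their treatment and gastroenterology care.
- *That the day counts measure risk.* They measure how long the rule is silent. The number of MIE children who enter on constipation medicine is not given.
- *That weekly diary checks in the MIE arm are the natural remedy.* The diary supplies the primary outcome. Calls to one arm about blank days would give that arm extra contact and cleaner outcome data.

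What the reply does not answer is that the general routes depend on someone deciding that a gap matters. None of the text shown makes days without a movement a reason for medical review at home, although the protocol did so in clinic.

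**Conclusion.** The point holds as a gap in the written safeguard. Prescribed constipation medicines stop in the MIE arm with no stated restart point, and the trigger for gastroenterologist review lapses for about 140 days before Week 28 (126 to 154). If treatment means the clinic phase only, a further 18 to 38 days before Week 8 are uncovered (about 28 to 31 nominal).

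This rests on three assumptions: that visits fall within the stated windows, that the clinic phase ends between day 11 and day 17, and that the handout and consent pages not shown do not already carry the instruction. If they do, the protocol needs only to say so.

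A reader might infer that the primary comparison is compromised. The documents do not support that: on the wide reading nothing is uncovered before the Week 8 endpoint, and no sample size, power or significance level depends on the trigger. This is a cheap safety improvement.

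**What to change.** 1. In Treatment (Weeks 3-4), state that the more-than-three-days trigger continues after clinic discharge to Week 28.
2. At discharge, tell MIE caregivers to contact a named unblinded team member when the limit is passed. The gastroenterologist then reviews the child and may restart the earlier medicine. Say that such contact does not by itself end participation. Caregiver contact also covers the 18 weeks without a diary, and the scripted calls stay as they are.
3. Record any restart in an unblinded log. Table 1.0 assigns the Concomitant Medication Log to the blinded independent evaluator, so an entry there could hint at allocation. The Safety Review still asks about new medicines, so this reduces the clue without removing it.
4. Add no diary checks or blank-day calls for the MIE arm alone. If diaries are checked at all, check them identically in both arms.

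The cost is a few sentences, one discharge instruction and one additional log. The downside is that a few laxatives may restart before Week 8, which the protocol says may interfere with learning to push. The Treatment section already permits such additions during treatment, and the log makes them reportable.

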Reminder Calls: During the 18 Week Home Implementation Phase, the study team will make monthly, scripted phone calls to participants. These phone calls will serve to remind the parents to continue to implement the intervention procedures they were taught and to confirm that they have an adequate supply of study medication. These calls will be scripted and parents will not be given any additional insight or clinical guidance. If necessary, parents will be reminded that they are participating in a research study and that the goal is to determine the intervention's effectiveness up to their Week 28 Follow Up visit. Parents will also be reminded that they will receive clinical guidance after completion of their Week 28 visit. However, the study team may intervene clinically and terminate study participation if they feel the child is in need of immediate emergency medical treatment.

Visit Windows

The visit window between Characterization/Medical Assessment and Baseline/MIE Treatment or the TAU consultation visits is 12 – 21 days. MIE Treatment or the TAU consultation visit must occur after the Week 2 Baseline. During this time, parents must collect a minimum of 7 days of toileting home data. These days do not need be consecutive.

The Week 4 Midpoint visit will occur 7-21 days after the Week 2 Baseline Visit (2 weeks +/- 7 days). The Week 8 Endpoint visit will occur 35-49 days after the Week 2 Baseline Visit (6 weeks +/- 7 days). Week 28 Follow Up will occur 175-189 days after the Week 2 Baseline Visit (26 weeks +/- 7 days).

Study Measures

Characterization Measures:

Autism Diagnostic Observation Schedule (ADOS; Lord et al., 2000) The ADOS is an

investigator-based procedure that places the child in naturalistic social situations demanding specific social and communication reactions. The ADOS provides a sample of the child's behavior in a naturalistic setting. Behaviors are coded in the areas of social communication, social relatedness, play and imagination, and repetitive behaviors. The ADOS contributes to the DSM 5 diagnosis of ASD.

Autism Diagnostic Interview-Revised (ADI-R) (Rutter, LeCouteur, & Lord, 2003). The ADI-R is a structured interview that is used to diagnose autism. The interview can be administered to a caregiver and is composed of 93 items. The instrument includes the three functional domains related to ASD: Language and Communication, Reciprocal Social Interactions, and Restricted, Repetitive, and Stereotyped Behaviors and Interests.

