If questions arise about a subject's possible deterioration, the situation will be discussed at the weekly team meeting. If the team determines that the subject's symptoms are becoming distressing or dangerous, we will hold a clinical conference with the participants caregiver and determine the best course for the subject. This may include withdrawal from the study in order to institute a treatment plan.

NOTE: In keeping with the intention to treat principle, we will ask parents of subjects who withdraw from treatment to return for study assessments and the subject's data will be analyzed with the original randomized group.

Safety Review: A safety review for adverse effects and concomitant medications will be conducted at baseline and every assessment visit by the IE. To accomplish this systematic review, the IE will use the Safety Review Form that has been used in several multi-site clinical trials in children with ASD. It contains a general inquiry about the child's health complaints, medical visits and new medications, and several questions about daily activities (e.g., sleep, appetite, energy level, and bowel and bladder functions) since the last study visit.

New adverse events (whether considered related to the treatment or not) will be rated mild, moderate or severe. The ratings: mild, moderate or severe are defined as follows:
mild= present, but no intervention required;
moderate= present, may be bothersome or may require intervention;
severe= present, bothersome and requires intervention.

All **new** adverse events (mild, moderate or severe) will be documented on the adverse event log. The status of previously-reported adverse events will be monitored as well. The adverse event log requires the independent evaluator to label the AE (a list of preferred terms will be provided) and to document the severity, onset, course, outcome, and attribution.

Decisions on the appropriate care of the subject will be made by the independent evaluator (who will be blind to treatment assignment) and the PI and in collaboration with the family's primary care provider as needed.

The attribution of reported AEs will be classified as follows:

- Definite: AE is clearly related to the study participation.
- Probable: AE is likely to be related to the study participation.
- Possible: AE may be related to the study participation.
- Unlikely: AE is doubtfully related to the study participation.
- Unrelated: AE is clearly not related to the study participation.

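### No adverse-event enquiry is scheduled for the 126 to 154 days between Week 8 and Week 28, and the call rules and deterioration rules for that period are not reconciled

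*Combined protocol and SAP*

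**What the plan says.** **When harm is asked about.** Table 1.0 marks the Adverse Event and Safety Review rows at Baseline and Weeks 4, 8 and 28. The Safety Review paragraph agrees: "A safety review for adverse effects and concomitant medications will be conducted at baseline and every assessment visit by the IE". Its questions reach back over the period "since the last study visit".

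**Home treatment.** Under Home Implementation, MIE families leave on one of three daily suppository regimens and "will be given a 30-day supply of study medication", or the equivalent for two a day. Intervention Content sets no end date: "they are instructed to continue to implement the intervention until independent continence is achieved".

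**Contact after Week 8.** Reminder Calls plans monthly scripted calls over an 18-week phase, with two stated purposes: to remind parents to keep using the procedures and to confirm that they have enough study medication. It adds that "These calls will be scripted and parents will not be given any additional insight or clinical guidance". Guidance is promised after the Week 28 visit, and the stated exception is a need for immediate emergency care. Table 2.0 leaves the home diary blank for 18 weeks under the label *No Contact*, then resumes it for a two-week follow-up.

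**Deterioration.** Adverse Event Collection and Reporting sends questions of possible deterioration to the weekly team meeting, and then: "If the team determines that the subject's symptoms are becoming distressing or dangerous, we will hold a clinical conference". It is not restricted to any study phase.

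**The concern.** The longest interval without a scheduled question about harm falls when children are treated at home by caregivers and seen least. The adverse reactions that Risk of Participation lists for glycerin suppositories are cramps, rectal irritation and tenesmus. Mild or passing events of this kind are easily forgotten or misdated when first asked about months later. The protocol itself notes, in the rationale for its constipation criteria, that many of these children cannot report pain verbally, so detection depends on asking the caregiver.

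Suppository use is also not recorded at home during the 18 weeks, so an event recalled at Week 28 could not readily be related to what the child was using when it occurred. The six-monthly reviews of adverse events and of the data set can act only on what has been collected.

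The second issue is operational. A caller following Reminder Calls and a colleague following the adverse-event section could handle the same non-emergency report differently.

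**Working it through.** **Inputs (Visit Windows, days after the Baseline Visit).** Week 8: day 35 to 49, nominal 42. Week 28: day 175 to 189, nominal 182.

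**The plan's own figure.** Table 2.0 gives 18 weeks of *No Contact* plus 2 weeks of follow-up, which is 20 weeks. From the windows, 182 − 42 = 140 days, and 140 / 7 = 20 weeks. The two agree.

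**Gap between scheduled enquiries (Week 28 day minus Week 8 day).**
- Shortest: 175 − 49 = 126 days = 18.0 weeks.
- Nominal: 182 − 42 = 140 days = 20.0 weeks.
- Longest: 189 − 35 = 154 days = 22.0 weeks.

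The final two-week diary lies inside this gap. It records bowel movements and medication use, not adverse events, so it does not shorten the enquiry gap. It does shorten the stretch with no record of use, to 16, 18 and 20 weeks respectively.

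**Does suppository use extend into the gap?** The baseline measures are taken on the first day of treatment. Ten visits at five a week end at about day 11, and the protocol allows 17 days. A 30-day supply would then last to day 11 + 30 = 41 or day 17 + 30 = 47, close to the Week 8 visit. The monthly supply check over the following 18 weeks shows that longer use is foreseen for some children. The documents do not say how many.

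**What the existing calls could do.** Eighteen weeks is 126 days. At one call every 28 to 30.4 days, that allows 126 / 30.4 = 4.1 to 126 / 28 = 4.5, so about four calls. Suppose four calls at 30-day spacing, the first 30 days after Week 8. The fourth falls 120 days after Week 8, leaving 126 − 120 = 6, 140 − 120 = 20 or 154 − 120 = 34 days to Week 28. The longest recall period is then 30 to 34 days, about one month.

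**The two action rules side by side.**

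| | Reminder Calls | Adverse Event Collection and Reporting |
|---|---|---|
| Scope | 18-week home phase | No phase stated |
| Trigger | Need for immediate emergency care | Possible deterioration; then distressing or dangerous symptoms |
| Action | Team may intervene and end participation | Team discussion; then a conference with the caregiver, possibly withdrawal |
| Refers to the other | No | No |

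**The case against.** Several stronger readings are tempting, and the documents do not support them.

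- **That harm in the gap is never sought.** The Week 28 Safety Review asks about the whole period since the previous visit, and a Concomitant Medication Log is completed then. The weakness is long recall, not absence of enquiry.
- **That children have 18 to 22 weeks of suppository exposure.** Those figures are calendar time between enquiries. Suppositories go home only with MIE families, and the instruction to continue ends at independent continence. The background describes fading the medication out.
- **That exposure is wholly unrecorded.** The last two weeks record medication use, and a log tracks doses taken from storage. That log shows what left the cabinet, not what was used at home.
- **That the calls ask nothing about harm.** The script is not in the documents. One can say only that the described purposes include no such question.
- **That a non-emergency report has no route, or that the two sections flatly contradict each other.** The study team makes the calls and meets weekly, and nothing suspends the deterioration rule. The withheld guidance can be read as coaching on the toileting procedures, and the emergency sentence concerns ending participation as well as intervening. This is an unreconciled ambiguity.
- **That serious risks are prominent.** Vomiting and electrolyte disturbance are listed only for bisacodyl and labelled rare. Most children are expected to go home on one glycerin suppository a day. No stated aim or analysis claims safety of prolonged home use.

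What stands after all this is a recall period of four to five months, no home record of suppository use for 18 weeks, and two action rules that do not mention each other.

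**Conclusion.** The point holds as a cheap improvement to safety data and clarity, not as a flaw in the efficacy design. The enquiry gap of 126 to 154 days (nominally 140) follows directly from the protocol's windows and needs no outside assumption. Three parts rest on inference: that the unseen call script matches its description, that some MIE children continue suppositories past Week 8 (suggested by the supply check, number unknown), and that calls about 30 days apart would bring recall down to about one month. The Week 8 primary endpoint is unaffected. The two action rules and the *No Contact* label need reconciling. Which threshold should govern is for the study team, and no view is taken here.

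**What to change.** - Add fixed questions to the existing monthly script, worded identically in both arms: any new health problem, medical visit or new medicine since the last contact, and any suppositories used (type and number).
- Have the caller or coordinator, not the independent evaluator, record positive answers and pass them to the PI and the weekly team meeting. The evaluator completes the adverse-event log and is blind, so enter events there in a form that does not reveal treatment assignment. Keep the suppository answers in the unblinded records.
- The study team should reconcile the action thresholds in Reminder Calls and in Adverse Event Collection and Reporting, with a cross-reference between them.
- Reconcile the *No Contact* label in Table 2.0 with the scheduled calls.

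The cost is a script change and a few more minutes on calls already planned. More minor events will be logged, and the extra contact could have a small effect on Week 28 outcomes. Identical wording in both arms limits any imbalance.
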